9.4.2 Secondary Endpoints

Secondary efficacy endpoints assess the effect of IV Ampion compared to SOC on the clinical outcomes for participants with COVID-19 on supplemental oxygen. The secondary endpoints will be tested in a hierarchical manner in the order presented, and thus no adjustment to the alpha level is necessary:

Objective	Endpoint
Secondary Endpoints	
Assess the effect of Ampion compared to placebo on safety	
Incidence of adverse events (AEs) and serious adverse events (SAEs) from baseline to Day 60.
Assess the effect of Ampion compared to placebo on clinical improvement	
Change in ordinal scale from baseline through Day 7.Change in ordinal scale from baseline to hospital discharge or day 14 (whichever occurs first).Change in ordinal scale from baseline to hospital discharge or day 28 (whichever occurs first).Change in NEWS2 score from baseline through Day 5.Change in NEWS2 score from baseline to hospital discharge.Modulation of cytokine levels from baseline to Day 5.
Assess the effect of Ampion compared to placebo on duration of respiratory failure to ventilator-free days.	
Percentage of participants who progress to respiratory failure (i.e., need for mechanical ventilation, ECMO, non-invasive ventilation) by Day 28.

Objective	Endpoint
Assess the effect of Ampion compared to placebo on intensive care	
Percentage of participants who require Intensive Care Unit (ICU) admission by Day 28.ICU-free days through Day 28.ICU LOS from ICU admission to discharge.
Assess the effect of Ampion compared to placebo on hospital stay	
Hospital length of stay (LOS) from admission to discharge.Hospital-free days through Day 28.
Assess the effect of Ampion compared to placebo on oxygen use	
Duration of oxygen use, blood oxygen saturation, and oxygen flow rate from baseline through Day 5.

The efficacy endpoints will be evaluated to estimate the treatment effect and use descriptive statistics including mean, standard deviation, percentages, minimum/maximum, and 95% confidence intervals. All endpoints will be tabulated and presented by treatment arm, cohort (severe and critical), and timepoint. Where appropriate, data will be tabulated and presented cumulatively across cohorts and/or timepoints.

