All binary outcomes are single incident percentages and thus the differences between the treatment groups will be tested using Fisher's exact test. The length of stay endpoints are also single incident endpoints the differences between the treatment groups will be tested using two sample t-test. All the other change from baseline variables are repeated assessments and will be analyzed utilizing a repeated measures analysis of variance.

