3.2 Secondary Endpoints

3.2.1 Change in ordinal scale from baseline through Day 7, Day 14 and Day 28.

The hypotheses to be tested are:

$$H_0: \mu_A = \mu_S \text{ versus } H_A: \mu_A \neq \mu_S$$

Where μ_A and μ_S represent the ordinal scale shift through day 7, 14, and 28 for Ampion and Placebo after randomization. The difference between Ampion and Placebo with respect to the change from baseline at day 7, 14, and 28 will be tested utilizing a Wilcoxon rank-sum test via PROC NPAR1WAY. To assess any potential time trends, an exploratory repeated measures analysis of variance will be performed with terms for treatment, time and the interaction between the two. This will be done utilizing PROC GLM with the REPEATED option.

3.2.2 Change in NEWS2 score from baseline through Day 7, or discharge if earlier.

The hypotheses to be tested are:

$$H_0: \mu_A = \mu_S \text{ versus } H_A: \mu_A \neq \mu_S$$

Where μ_A and μ_S represent the mean change from baseline in the NEWS2 score assessment through day 7 for Ampion and Placebo after randomization. The difference between Ampion and Placebo with respect to the change from baseline at day 7, or discharge if earlier, will be tested utilizing a Wilcoxon rank-sum test via PROC NPAR1WAY. To assess any potential time trends an exploratory repeated measures analysis of variance will be performed with terms for treatment, time and the interaction between the two. This will be done utilizing PROC GLM with the REPEATED option.

3.2.3 Percentage of participants who progress to respiratory failure by Day 28.

The hypotheses to be tested are:

$$H_0: \pi_A = \pi_S \text{ versus } H_A: \pi_A \neq \pi_S$$

Statistical Analysis Plan (SAP) for Clinical Study AP-017

Let π_A and π_S represent the percentage of patients who have respiratory failure for Ampion and control during the first 28 days after randomization.

This difference will be tested utilizing the appropriate chi-square test or Fisher's exact test utilizing PROC FREQ with the EXACT option, if needed.

Also, the median time to respiratory failure will be tested for difference between the two groups via the log-rank test. The log-rank test will be performed using PROC LIFETEST; and the estimation of the time-to-event distributions will be performed using the method of Kaplan and Meier.

3.2.4 Percentage of participants who require Intensive Care Unit (ICU) admission by Day 28; ICU-free days through Day 28; ICU length of stay (LOS) from ICU admission to discharge.

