There are two endpoints in this set. Hypotheses about both will be tested independently. The first hypothesis about the percentage of patients who are admitted to the ICU involves all patients. The second hypothesis involves only patients who are admitted to the ICU. Since it is not known how many many patients will be admitted to the ICU, the testing of the second hypothesis will be considered exploratory and not part of the hierachial testing scheme.

The first hypotheses to be tested is:

$$H_0: \pi_A = \pi_S \text{ versus } H_A: \pi_A \neq \pi_S$$

Where π_A and π_S represent the percentage of patients who are admitted to the ICU for Ampion and Placebo during the first 28 days after randomization. The difference between Ampion and Placebo will be tested via an appropriate chi-square test or Fisher's exact test utilizing PROC FREQ with the EXACT option, if needed.

The second hypothesis to be tested is:

$$H_0: \text{Median}_A = \text{Median}_S \text{ versus } H_A: \text{Median}_A \neq \text{Median}_S$$

Where Median_A and Median_S are the median ICU length of stay for the Ampion and placebo groups. Assuming there is no censoring, this will be tested using the Wilcoxon rank sum test via PROC NPAR1WAY. If censoring occurs, e.g., death, then the log rank test will be used based on PROC LIFETEST.

3.2.5 Modulation of cytokine levels from baseline to Day 5.

The hypotheses to be tested are:

$$H_0: \mu_A = \mu_S \text{ versus } H_A: \mu_A \neq \mu_S$$

Where μ_A and μ_S represent the mean percent change from baseline in the cytokine levels at day 5 for Ampion and Placebo after randomization. The difference between Ampion and Placebo with respect to the percent change from baseline at day 5 will be tested utilizing a two sample t-test via PROC TTEST. To assess any potential time trends an exploratory repeated measures analysis of variance will be performed with terms for treatment, time and the interaction of the two. This will be done utilizing PROC GLM with the REPEATED option.

Statistical Analysis Plan (SAP) for Clinical Study AP-017

3.2.6 Hospital length of stay.

The hypotheses to be tested are:

$$H_0: \text{Median}_A = \text{Median}_S \text{ versus } H_A: \text{Median}_A \neq \text{Median}_S$$

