5.1.2 Intent to Treat (ITT) Analysis Set

The intent-to-treat (ITT) analysis population is defined as all randomized patients. All efficacy analyses will be performed in the ITT population. Patients will be analyzed as randomized.

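### The SAP's exploratory time-trend analyses use a complete-case procedure (PROC GLM REPEATED), and the protocol and SAP name different tests for the change endpoints without declaring it

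*SAP*

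**What the plan says.** SAP 3.2.1 (ordinal scale), 3.2.2 (NEWS2) and 3.2.5 (cytokines) each name a main test and then a secondary look at time.

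- **Ordinal scale:** the arms are compared "with respect to the change from baseline at day 7, 14, and 28 will be tested utilizing a Wilcoxon rank-sum test via PROC NPAR1WAY".
- **NEWS2:** the comparison is made "with respect to the change from baseline at day 7, or discharge if earlier, will be tested utilizing a Wilcoxon rank-sum test via PROC NPAR1WAY".
- **Cytokines:** the comparison is made "with respect to the percent change from baseline at day 5 will be tested utilizing a two sample t-test via PROC TTEST".
- **Time trends:** SAP 3.2.1 reads "To assess any potential time trends, an exploratory repeated measures analysis of variance will be performed with terms for treatment, time and the interaction between" (treatment by time). Its next sentence names the procedure: "This will be done utilizing PROC GLM with the REPEATED option". SAP 3.2.2 and 3.2.5 repeat the same plan.

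SAP 5.1.2 states: "All efficacy analyses will be performed in the ITT population".

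Protocol 9.4.2 assigns Fisher's exact test to binary outcomes and a t-test to length of stay, and then says: "All the other change from baseline variables are repeated assessments and will be analyzed utilizing a repeated measures analysis of variance". It names no SAS procedure. It places these endpoints in a sequence: "The secondary endpoints will be tested in a hierarchical manner in the order presented, and thus no adjustment to the alpha level is necessary".

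SAP Section 9, on changes from the protocol, lists the new primary endpoint and the ordering of the secondary endpoints. It does not list a change of test.

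**The concern.** PROC GLM with a REPEATED statement treats each patient's visits as one response vector and discards the patient if any element is missing. A patient with six of seven daily values contributes nothing. The result no longer describes all randomized patients, which is what SAP 5.1.2 promises.

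The deletion would matter less if gaps were haphazard. In this trial, death and early discharge are themselves outcomes of treatment. Where either one stops the measurements, the retained group is selected after randomization, and the fastest recoveries and the worst courses can both be missing from it. A time trend in such a group need not reflect the effect of treatment.

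The second issue is which test counts. The change endpoints sit in a hierarchical scheme in both documents, so each needs one identified test. With two different tests on file and no declared change, a result that is significant by one and not by the other leaves it unclear whether testing may continue down the sequence.

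**Working it through.** **Plan's own figures.** Neither document gives a missingness rate, power or sample size for the change endpoints. The only power figure is for the primary endpoint: 81.3% for 8% versus 22% with 100 per arm. Enumerating all binomial outcomes with the unpooled z-test gives 81.28%, so it reproduces. This point does not affect it.

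**Is there a missing-data rule?** SAP 7.1 covers dates of adverse events and medications, and one sensitivity analysis of the primary endpoint. Protocol 9.5 covers adverse-event data and mortality. Neither says how a death, a discharge or a missed visit enters the ordinal, NEWS2 or cytokine analyses.

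**NEWS2.**
- Protocol 5.2 builds the score from oxygen requirement, SpO2 and vital signs. It has no value for a dead patient.
- SAP 2.3 has contact after treatment typically by telephone unless the patient is an inpatient.
- Both schedules list NEWS2 at Days 28 and 60, and the SAP schedule also lists it at a Day 7 follow-up. Neither marks vital signs at any follow-up visit. Protocol 5.2 does mention vital signs at follow-up, taken from medical records.
- Protocol 7.1 ends treatment at discharge if that comes first, and SAP 3.2.2 allows for discharge before Day 7, so early discharge is expected.

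A Day 1 to Day 7 analysis would therefore probably keep mainly patients still in hospital on Day 7. If 10%, 30% or 50% of 200 patients had no NEWS2 after early discharge (assumed), 200 × (1 − share) = 180, 140 or 100 would remain.

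**Ordinal scale.**
- Protocol 5.2 gives death a score of 8, and scores 0 to 2 do not require a hospital stay. The scale is to be recorded at every visit to Day 60. Deaths and discharges can therefore be scored.
- No rule says that an 8 recorded at death is entered at later visits.
- The SAP schedule has a Day 14 visit and the protocol schedule does not. If sites follow the protocol, Day 14 values may often be absent, and each gap removes the whole patient from a model that includes Day 14.

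**Cytokines.** Protocol 5.2 plans samples at baseline, Day 5 and discharge. For the single change to Day 5, a t-test and a repeated-measures model lose the same patients. The procedure matters only if the discharge sample is included.

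**Size under random gaps alone (illustration).** With an independent missing probability m at each of k visits, the share of patients deleted is 1 − (1 − m)^k. Both m and independence are assumptions.

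| Visits | m = 3% | m = 5% |
|---|---|---|
| k = 3 (Days 7, 14, 28) | 1 − 0.97³ = 8.7% | 1 − 0.95³ = 14.3% |
| k = 9 (Days 1–7, 14, 28) | 1 − 0.97⁹ = 24.0% | 1 − 0.95⁹ = 37.0% |

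**What deleting deaths would do to the ordinal change (illustration).** Suppose survivors do equally well in both arms, with mean baseline 4.3 and mean final score 1.75, and that 25%, 50% or 100% of the planned 8% and 22% events are deaths (all assumed). A survivor changes by 1.75 − 4.3 = −2.55, and a death scored 8 changes by 8 − 4.3 = +3.7. The arm difference is (death rate on Ampion − death rate on control) × 6.25:

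- 2% vs 5.5%: −0.035 × 6.25 = −0.22
- 4% vs 11%: −0.07 × 6.25 = −0.44
- 8% vs 22%: −0.14 × 6.25 = −0.875

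In 5,000 simulated trials per setting, Wilcoxon tests with deaths scored 8 rejected in 7%, 14% and 41%. With deaths deleted, the mean difference was about zero and a t-test rejected in about 5%. Deletion removes the mortality effect completely, so the scoring rule needs to be written down.

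**Test named for each endpoint.**

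| Endpoint | Protocol 9.4.2 | SAP 3.2 |
|---|---|---|
| Ordinal change | Repeated-measures ANOVA | Wilcoxon |
| NEWS2 change | Repeated-measures ANOVA | Wilcoxon |
| Cytokine change | Repeated-measures ANOVA | t-test |

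**The case against.** The strongest reply is that little depends on this procedure. The SAP calls the analysis exploratory, and protocol 9.1 leaves analytic detail to the SAP. The SAP's NEWS2 test uses the value at discharge when that comes before Day 7, so it keeps early discharges. All of this stands, and it limits the consequence.

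Three stronger readings are tempting, and the documents do not support them.

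- **That the protocol makes PROC GLM REPEATED the main test.** This joins the SAP's procedure to the protocol's status for the method. The protocol names no procedure, and a mixed model is also a repeated-measures analysis. No document makes the complete-case run confirmatory.
- **That deaths and early discharges necessarily drop out.** This is not shown for the ordinal scale, where both can be scored. For NEWS2 it is a probable inference from the schedule. The documents do not state it, and they do list NEWS2 at follow-up visits.
- **That a quarter to a third of patients would be lost.** The 24% and 37% figures need nine visits and independent gaps. SAP 3.2.1 tests three days. Days 1 to 5 are in-person treatment days, when gaps should be fewest, and gaps that cluster within patients delete fewer of them.

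It is also fair to say that a mixed model does not solve the problem of death. Under missing at random it implicitly models values after death, so it needs a scoring rule beside it.

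**Conclusion.** The point holds as two limited defects.

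First, the exploratory time-trend analyses in SAP 3.2.1, 3.2.2 and 3.2.5 use a procedure that drops every patient with an incomplete set of visits, which conflicts with the ITT statement. For NEWS2 the loss is probably related to outcome. For the ordinal scale it depends on missed visits and on an unstated rule for death. For cytokines it arises only beyond the single Day 5 comparison. The size cannot be fixed from the documents: under assumed independent missingness of 3% to 5% per visit, it runs from 8.7% to 14.3% over three visits and from 24% to 37% over nine.

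Second, the protocol and the SAP name different tests for endpoints in the hierarchical sequence, and SAP Section 9 does not disclose it. This needs no assumption.

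The primary analysis is untouched. Once the tests of record are settled, the choice of procedure affects exploratory results only, so this is a minor but inexpensive improvement.

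**What to change.** 1. In SAP 3.2.1, 3.2.2 and 3.2.5, replace PROC GLM REPEATED with a mixed model (PROC MIXED) on all available visits, with treatment, visit, treatment-by-visit, baseline value and severity stratum. Name the visits and the covariance structure in advance. An unstructured matrix over nine visits has 9 × 10 / 2 = 45 parameters, so a fallback is sensible.
2. State that death is carried forward as score 8 at every later ordinal visit, and how discharged patients are scored. State that the NEWS2 model describes values while patients are alive and in hospital.
3. Keep the SAP's Wilcoxon tests and t-test as the tests of record, amend protocol 9.4.2 to match, and declare the change in SAP Section 9.
4. Reconcile the Day 14 ordinal assessment between the two schedules. No model can recover a visit that was never made.

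The cost is wording and a little more programming. The mixed model brings a missing-at-random assumption, which is weaker than what the complete-case analysis needs but cannot be tested.

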5.2 Assessment Methods

Demographic Data

Demographic data will be collected from medical records: age, gender, race, height and weight, comorbidities.

Medical History

Medical history and pre-existing conditions will be collected from medical records.

Concomitant Medications

Concomitant medications will be collected from the medical records: prior (pre-hospitalization) concomitant medications, in-patient concomitant medications.

Mortality

All-cause mortality will be recorded at hospital discharge, Days 28 and 60, as applicable. Cause of mortality will be assessed and documented. All-cause mortality is calculated for the primary endpoint as the percentage of participants with a successful outcome (life) or unsuccessful outcome (death).

Length of Stay (LOS)

Due to the COVID-19 health emergency, the Centers for Medicare and Medicaid is temporarily allowing long-term care facilities not normally used as a resident's room to accommodate beds and residents for care in emergencies/situations needed to help with surge capacity. Therefore, hospitalization refers to hospital and/or inpatient care during the COVID-19 health emergency. Inpatient care may include hospitals treating COVID-19 patients; dedicated COVID-19 treatment facilities with 24/7 care; and/or dedicated research facilities with 24/7 care.

Dates of hospitalization and ICU admission as well as discharge dates will be recorded at hospital discharge, Days 28 and 60, as applicable. The hospital LOS and ICU LOS will be calculated as follows:

- ICU admission: defined (in days) as the first study day when ICU status is changed to “yes” minus baseline date + 1
- Hospital LOS: is defined (in days) as the date of hospital discharge minus date of hospital admission + 1
- ICU LOS: defined (in days) as the date moved out of ICU minus first study date when ICU admission changed to “yes” + 1

Oxygen Use

Oxygen use measured as blood oxygen saturation (SpO2) and oxygen flow rate (liters per minute, lpm) will be recorded at every visit from baseline to Day 5.

Intubation/Extubation

Date and time of intubation/extubation and days on ventilator will be recorded at hospital discharge, Days 28 and 60, as applicable. Proportion of participants who progress to respiratory failure (i.e., need for mechanical ventilation, ECMO, non-invasive ventilation, or high-flow nasal cannula oxygen) will be evaluated.

Vital Signs

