2.3 Study design

Statistical Analysis Plan (SAP) for Clinical Study AP-017

This is a Phase II randomized, double-blinded, placebo-controlled study to evaluate the safety and efficacy of IV Ampion in participants with COVID-19 who require supplemental oxygen.

Participants will be randomized 1:1 to active or placebo using a random allocation sequence stratified by disease severity.

All subjects receiving test product will also receive the standard of care (SOC) for COVID-19, which includes:

- Oxygen administration to maintain oxygen saturation of 90% or greater.
- Nursing physical that may include review of neurological; pulmonary; cardiac; gastrointestinal; and urinary assessment at least daily during treatment.
- Vital monitoring (heart rate, blood pressure, temperature, respiratory rate, SpO2) at least daily during treatment.
- Telemetry monitoring to evaluate heart rhythm and rate.
- Diet as tolerated to satisfy nutritional needs.
- Treatments for COVID-19 symptoms including antibiotics, cough suppressants/expectorants, anti-coagulants, fever reducers/pain killers, anti-nausea drugs, and/or bronchodilators.
- Treatments for COVID-19 as approved by the FDA including expanded access, emergency, or compassionate use (i.e., remdesivir, dexamethasone).
- Medications will be recorded as concomitant medication, tabulated, and compared among groups.

The clinical effects, safety, and tolerability of treatment will be evaluated from baseline to Day 28 and through Day 60. Evaluations at screening and during the 5-day treatment occur in person. Evaluations after the 5-day treatment to the end of the study (days 7 to 60) will typically occur via telephone contact unless the patient is in an inpatient setting.

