2.4 Sample Size

The trial is designed to enroll up to approximately 200 patients across two treatment arms (active or control), with 100 subjects per arm, randomized 1:1 using a random allocation sequence stratified by COVID-19 disease severity (severe or critical). An interim analysis of the data is planned after 30 subjects (approximately n=15 subjects per arm) to evaluate the relative effect. At the interim analysis, the sample size may be re-estimated to determine the additional number of patients required for adequate power to meet the chosen effect size for the primary endpoint.

The number of participants is selected based on the effects observed for the primary endpoint, prevention of need for mechanical ventilation or death prior to day 28. A study recently reported in Lancet Respiratory Medicine with 243 hospitalized patients receiving the placebo for COVID-19 found 22% did not achieve day 28 ventilation-free survival (Lancet Respir Med 2021; [https://doi.org/10.1016/S2213-2600\(21\)00494-X](https://doi.org/10.1016/S2213-2600(21)00494-X)). In the AP-014 study, a lower rate (8%) was observed for subjects receiving inhaled Ampion. Assuming the same proportions (8% for Ampion and 22% for control) by Day 28, with 100 subjects per group, a two-sided 5% significance level, and using a z-test with unpooled variances, then under binomial enumeration the power to detect this difference is about 81.3%.

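### Respiratory failure and ICU admission by Day 28 (SAP 3.2.3 and 3.2.4) leave death out of the event, so a patient who dies without that care is scored like one who recovers

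*SAP*

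**What the plan says.** For respiratory failure, SAP 3.2.3 defines parameters that "represent the percentage of patients who have respiratory failure for Ampion and control during the first 28 days after randomization". They are compared by chi-square or Fisher's exact test, and a log-rank test with Kaplan-Meier curves is added for time to respiratory failure. For ICU admission, SAP 3.2.4 defines parameters that "represent the percentage of patients who are admitted to the ICU for Ampion and Placebo during the first 28 days after randomization". SAP 5.1.2 puts all randomized patients in every efficacy analysis.

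The SAP does not itself define respiratory failure. Protocol 9.4.2 has "Percentage of participants who progress to respiratory failure (i.e., need for mechanical ventilation, ECMO, non-invasive ventilation) by Day 28", and the synopsis and Protocol 3.3.2 agree. Protocol 5.2, under intubation and extubation, is wider: "i.e., need for mechanical ventilation, ECMO, non-invasive ventilation, or high-flow nasal cannula oxygen". Neither definition includes death.

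Elsewhere the plan does count death. The primary endpoint is mechanical ventilation or death by Day 28 (SAP 3.1), and death is score 8 on the ordinal scale (Protocol 5.2). SAP 8.6 tests the secondary endpoints hierarchically in Section 3.2 order, which puts respiratory failure third and ICU admission fourth. SAP 3.2.4 removes only ICU length of stay from that sequence.

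**The concern.** Both endpoints record use of a form of care. Death can prevent that use while being a worse result. With a denominator of everyone randomized and no rule for death, a patient who dies on low-flow oxygen on the ward is a non-event on both endpoints, as is a patient discharged well.

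The log-rank test raises the same issue. With respiratory failure as the only event, a prior death can enter only as a censored time, which treats the patient as still able to progress.

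Both percentages are formal steps in the hierarchy. At stake is a claimed benefit on respiratory failure or ICU use that partly reflects patients dying before, or instead of, receiving that care.

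**Working it through.** **1. The plan's own figure.** The only stated power is for the primary endpoint (SAP 2.4): "Assuming the same proportions (8% for Ampion and 22% for control) by Day 28, with 100 subjects per group", with "a two-sided 5% significance level, and using a z-test with unpooled variances", and "under binomial enumeration the power to detect this difference is about 81.3" per cent. Summing the joint binomial probabilities over all pairs of counts with |p1 − p2| / √(p1(1−p1)/100 + p2(1−p2)/100) > 1.96 gives 0.8128, so the figure reproduces. Nothing comparable is stated for respiratory failure or ICU admission.

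**2. Does any rule catch a known death?** SAP 7.1 replaces unknown status by death, for the primary endpoint only. Protocol 9.5 covers unknown mortality status only. Neither applies to a known death in SAP 3.2.3 or 3.2.4.

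**3. How deaths are scored, by support at death.**

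| Death without ventilation or ECMO | Protocol 9.4.2 (also synopsis, 3.3.2) | Protocol 5.2 |
|---|---|---|
| On low-flow oxygen | non-event | non-event |
| On high-flow cannula | non-event | event |

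**4. One constructed trial, 100 per arm (split assumed).** Respiratory failure is 10 on Ampion and 22 on control; deaths without that support are 14 and 2.

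- As written, 10 vs 22: χ² = 200 × (10×78 − 90×22)² / (100 × 100 × 32 × 168) = 5.36, p = 0.021 (Fisher 0.033), favouring Ampion.
- Counting death: 10 + 14 = 24 vs 22 + 2 = 24, p = 1.0.

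This split is deliberately extreme. With 16 vs 22 failures and deaths without support of 8 vs 2, the composite is again 24 vs 24, but the failure comparison is p = 0.28 (Fisher 0.37).

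**5. Range for the percentage test.** Control respiratory failure is assumed at 22%, borrowed from the primary endpoint's planning rate. Failure-or-death is equal in the two arms, and d points of Ampion's events are deaths without support in excess of control. The test then compares (22 − d)% with 22%. The table gives the chance of a two-sided 5% result favouring Ampion, by binomial enumeration of the pooled z-test (equivalent to Pearson chi-square).

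| d (points) | 0 | 2 | 4 | 6 | 8 | 10 | 12 | 14 |
|---|---|---|---|---|---|---|---|---|
| Chance | 2.5% | 5% | 11% | 19% | 32% | 48% | 65% | 81% |

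**6. Range for the log-rank test, if deaths are censored.** 2,000 simulated trials per scenario, with constant hazards, 100 per arm, failure-or-death 24% in both arms, and about 2% of control dying without support.

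| Ampion deaths without support | 2% | 7% | 12% | 14% |
|---|---|---|---|---|
| Log-rank on respiratory failure favours Ampion | 2.4% | 12.6% | 40.4% | 58.5% |

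The log-rank test on failure-or-death stays at 2.4% to 2.8% throughout.

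**The case against.** **Death is captured elsewhere, and earlier.** This stands and limits the impact. SAP 8.6 calls the secondary analyses supportive, and the ordinal scale, which scores death, comes first among them. If the primary endpoint gates the secondaries (implied, not stated outright) and the respiratory failures are all mechanical ventilation, equal failure-or-death means an equal primary endpoint, and formal testing would usually stop there. The protection is incomplete, because respiratory failure also includes non-invasive ventilation.

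**A reader might infer that every death without the event takes a point off that arm's rate.** It does not. The denominator is fixed, so such a death changes neither count. It lowers the rate only relative to what would have happened had that patient lived to receive the support, which need not hold for a sudden death after discharge.

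**A reader might infer that a death on high flow always counts as a success.** That holds under Protocol 9.4.2 but not under Protocol 5.2.

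**A reader might infer that the SAP orders censoring at death in 3.2.3.** It is silent there. Censoring is inferred from the single-event definition and from SAP 3.2.4 and 3.2.6, which give death as an example of censoring for length of stay.

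**Need could mean need without receipt.** The protocol speaks of needing ventilation and requiring ICU admission, so a patient with a do-not-intubate order might be counted. That is possible but unstated, and the SAP's ICU wording is actual admission.

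**The composite largely repeats the primary.** For respiratory failure this is fair; it is the real cost of the fix.

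**Conclusion.** The gap is real. Both endpoints give a known death without the support, or without an ICU stay, the value of a recovery, and no other rule corrects this. Deaths on low-flow oxygen are missed under either definition; deaths on high flow depend on which protocol section applies.

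The size cannot be fixed from the documents, which give no rate of death without support. An excess of 2 points of such deaths on Ampion barely matters (about 5% against 2.5%); 6 points gives about 19% and 10 points about 48%. These figures assume 22% control respiratory failure, equal failure-or-death in both arms, 100 per arm and a 5% level. Fisher's test, which Protocol 9.4.2 names for binary secondaries, would give somewhat lower chances. The log-rank figures also assume constant hazards and censoring at death.

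The documents do not support the stronger reading that these endpoints will mislead or that the trial's main conclusion is at risk: they are supportive secondaries, and the primary endpoint would show the deaths. The change should still be made, because it is cheap and aligns these endpoints with the primary.

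**What to change.** In SAP 3.2.3, SAP 3.2.4 and Protocol 9.4.2, with matching wording in the synopsis and Protocol 3.3.2:

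- Test respiratory failure or death by Day 28, and ICU admission or death by Day 28.
- Use the first composite as the event in the SAP 3.2.3 log-rank and Kaplan-Meier analyses.
- Report by arm each component and the number of deaths without the event.
- Reconcile the respiratory failure definitions in Protocol 5.2 and 9.4.2 on high-flow oxygen, and state the agreed one in the SAP.

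A cumulative incidence analysis with death as a competing event would describe the data properly, but could still favour the arm with more deaths, so it is not enough alone.

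The cost is SAP and protocol wording, made before any unblinded look. The required data are already in the schedule of assessments. The downside is more overlap with the primary composite, especially for respiratory failure.
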